1.3 Schedule of Assessments

Table 1 Schedule of Assessments

Assessments	Screening Period ^{††}	Treatment Period			Safety Follow-up Period
Day	-28 to -1	1 (Operation)			10 (Outpatient) ¹
Window		Preoperative	Intraoperative	Postoperative	
Visit Number	1		2		3
Informed Consent	X				
Inclusion/Exclusion Criteria	X				
Primary Diagnosis of Target Disease ²	X				
Medical History ³	X				
Demographics ⁴	X				
Drug and Alcohol Screen ⁵	X [†]				
Physical Examination ⁶	X	X		X	X
Vital Signs ⁷	X	X		X ⁸	X
Clinical Laboratory Tests ⁹	X [†]	X		X ⁸	X
Height ⁷	X				
Body Weight ⁷	X				X
Serum or Urine Pregnancy Test ¹⁰	X [†]				X
ECG ¹¹	X	X	X	X	X
Dosing ASP5354 ¹²			X		
Blood Sampling for ASP5354 Pharmacokinetics ¹³		X	X		
Confirmation of Urine or Skin Coloration ¹⁴			→	→	→
Investigator Evaluation for LN Visualization ¹⁵			X		
Record Surgery ¹⁶			X		
Previous/Concomitant Medications	X	X	X	X	X ¹⁷
AE Assessment	X	X	X	X	X ¹⁷
Study Participant Feedback Questionnaire	X				X

Footnotes and abbreviations on next page

AE: adverse event, ECG: electrocardiogram; IP: investigational product; IRT: interactive response technology; LN: lymph node; NIR-F: near-infrared fluorescence; TNM: tumor, nodes and metastases

† These assessments will be performed by a local laboratory and the results of these assessments must be obtained prior to participant enrollment.

†† The assessments scheduled for the screening period can be done on day 1 if all eligibility criteria can be confirmed prior to registration in the IRT and prior to treatment. If screening procedures are performed on day 1, physical examination, vital signs, clinical laboratory tests, ECG, previous/concomitant medications and AE assessment will be done once.

1. If a participant discontinues early from the study, day 10 outpatient visit procedures will be performed upon study discontinuation.
2. Primary diagnosis of the target disease will include:
 - Breast cancer: T categorization in TNM classification, location of tumor (left breast, right breast or other)
 - Melanoma: T categorization in TNM classification and location of tumor (Extremities [upper/lower, left/right], Trunk, Head and Neck, Other), Tumor Thickness and Ulceration status.
3. Medical History includes all significant medical conditions that have occurred or are currently ongoing. The medical condition, onset date, and recovery date will be collected.

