14. The occurrence of green coloration of the urine or skin will be monitored throughout the study. If observed, any visual green coloration abnormalities will be recorded as an AE. If it occurs for participants who have an urethral catheter in place, the color of urine will be assessed during surgery and every 120 minutes (\pm 30 minutes window) after the end of surgery until it resolves or the participant is discharged, whichever is earlier. If no urethral catheter is in place, voided urine will be assessed for green coloration and the time collected until it resolves or the participant is discharged, whichever is earlier. The start and stop date and time will also be recorded. The occurrence of green coloration of the skin will be recorded as an AE any time after dose administration. The start and stop date and time will be recorded. Skin coloration will be followed up until it resolves or the participant is discharged, whichever is earlier.

Footnotes continued on next page

15. Surgeon evaluation for LN(s) visualization includes incidence of visualization of the LN(s) and distal or second tier LN(s) and the Likert Scale for qualitative response of the intensity of fluorescence. After administration of ASP5354, visualization of the LN(s) will be assessed first using a NIR-F imaging system followed by confirmation with the gamma probe. Once lymphatic mapping is completed, gamma probe will be used per SoC. For all the LNs observed by ASP5354, gamma probe will be attempted to measure radioactivity. If the LN is not observed with NIR-F after approximately 15 minutes following injection for breast cancer participants and approximately 15 to 30 minutes for melanoma participants depending on the location of the tumor and LNs, the investigator can proceed to use the gamma probe for LN detection. When the LN is detected with the gamma probe first, radioactivity will be measured and then NIR-F imaging should be attempted again for LN visualization. During surgery, parameters will be recorded such as time of incision and number of LN(s).
16. Fluorescence images will be captured and recorded during the entire surgery and archived.

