2 INTRODUCTION

2.1 Study Rationale

The currently approved agents for lymphatic mapping, while effective, have negative consequences such as allergic reaction, tissue staining, radiation exposure and/or require special handling and disposal. An agent that is safe, easy to use and may shorten operative times without negative effects would be beneficial for both patients and surgeons.

ASP5354 is a small-molecule, near-infrared fluorescence (NIR-F) imaging agent that is an indocyanine green (ICG)-derivative conjugated with cyclodextrin. The physical and chemical properties differ from ICG and allow shorter transit times from injection to lymph node (LN) uptake than ICG in non-clinical studies.

ASP5354 will be evaluated in patients undergoing Standard of Care (SoC) lymphatic mapping to determine safety, optimal dose and preliminary efficacy in lymphatic mapping.

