7.2.6 Other Assessments

7.2.6.1 Green Coloration of Urine or Skin

The occurrence of green coloration of the urine or skin will be monitored throughout the study. If observed, any visual green coloration abnormalities will be recorded as an AE. If urine coloration occurs for participants who have a urethral catheter in place, the color of urine will be assessed during surgery and every 120 minutes (\pm 30 minutes window) after the end of surgery until it resolves or the participant is discharged, whichever is earlier. If no urethral catheter is in place, voided urine will be assessed for green coloration and the time collected until it resolves or the participant is discharged, whichever is earlier. The start and stop date and time will also be recorded. The occurrence of green coloration of the skin will be recorded as an AE any time after dose administration. The start and stop date and time will be recorded. Skin coloration will be followed up until it resolves or the participant is discharged, whichever is earlier.

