4.6 Other Endpoints

4.6.1 Green Coloration of Urine or Skin

The frequency and percentage of patients who experience green coloration of urine will be summarized by dose level and tumor type only for subjects who used urethral catheter. The duration of green coloration of urine or skin (in hours) will be summarized using descriptive statistics by dose level and tumor type. The duration is calculated from first date/time point of green coloration of urine or skin to last date/time point of green skin coloration. If the green coloration of urine or skin is still present at discharge, the duration is from first date/time point of green coloration to the date/time of discharge.

Additional to descriptive statistics, if applicable, the duration will be analyzed using Kaplan Meier estimation. For this purpose, subjects with green coloration of urine or skin at discharge are censored at the time point of discharge.

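### Follow-up of green coloration stops at discharge in some places and runs to day 10 in others, and the SAP counts color still present at discharge as a completed duration

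*Protocol*

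**What the plan says.** **Monitoring period.** Protocol 7.2.6.1, Table 1 footnote 14 and Table 10 footnote 7 all open with the same statement: "The occurrence of green coloration of the urine or skin will be monitored throughout the study". Any coloration seen is to be recorded as an AE, with start and stop date and time.

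**End of follow-up.** The same three places then set an earlier end.
- Skin: "Skin coloration will be followed up until it resolves or the participant is discharged, whichever is earlier".
- Urine without a catheter: "voided urine will be assessed for green coloration and the time collected until it resolves or the participant is discharged, whichever is earlier".
- Urine with a catheter: assessed during surgery and every 120 minutes (±30) "after the end of surgery until it resolves or the participant is discharged, whichever is earlier".

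**Schedule.** In Table 1 the row "Confirmation of Urine or Skin Coloration" carries three arrows, which by position are intraoperative, postoperative and safety follow-up (day 10). Table 10, the crisis schedule, covers visit 3 only and lists the same row with its own alternative way of collecting it.

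**General AE rules.** Protocol 7.3.1 collects all AEs from consent to the follow-up visit. Protocol 7.3.3 requires active follow-up at later visits or contacts after an AE is first reported.

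**Analysis.** SAP 4.6.1 summarizes duration in hours with descriptive statistics by dose level and tumor type. If the coloration "is still present at discharge, the duration is from first date/time point of green coloration to the date/time of discharge". A Kaplan-Meier estimate is added if applicable, with participants still colored at discharge censored at that time. The current Protocol 9.3.5.1 plans only the number and percentage of participants with coloration, so the duration summary exists in the SAP alone.

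**The concern.** Two problems meet here.

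The protocol gives sites two incompatible end points for the same observation. One site may close the coloration record at discharge; another may carry it to day 10 because the schedule and the AE rules say so. Stop dates would then mean different things at different sites.

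The SAP also fixes the shorter end point in the analysis, and in the descriptive statistics it treats an unresolved case as if the color had cleared at discharge. No individual duration can exceed the time from first coloration to discharge. If color persists longer at higher doses, the summary compresses the difference, because the longest durations are the ones cut.

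The point has some substance for this product. Protocol 2.1 says approved agents "have negative consequences such as allergic reaction, tissue staining, radiation exposure", the test product is itself a green dye injected under the areola or into the dermis, and safety and tolerability after local injection is a secondary objective. A reader of the clinical study report would expect a table of coloration duration to show how long color lasts.

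**Working it through.** **Step 1: passages side by side.**

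| Place | End of observation of coloration |
|---|---|
| 7.2.6.1, Table 1 footnote 14, Table 10 footnote 7, opening statement | whole study |
| Same three places, skin and urine rules | resolution or discharge |
| Table 1 row, third arrow | day 10 |
| Table 10 row (visit 3 only) | day 10 |
| 7.3.1 and 7.3.3, coloration being an AE | follow-up visit and later contacts |
| SAP 4.6.1, descriptive and Kaplan-Meier | discharge |

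Table 10 is the clearest evidence. It applies only to an outpatient visit on day 10. A participant attending it has normally left hospital, so a stop at discharge leaves that row almost nothing to record. No passage says which rule governs.

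**Step 2: what the SAP rule does to a duration.** Let T be the true duration and L the time from first coloration to discharge. The value entered is min(T, L). It is correct when T ≤ L and too short when T > L, so any bias in the descriptive summary is downward.

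**Step 3: illustration.** The documents give no time to discharge and no expected duration of coloration, so there is no figure of the plan's own to reproduce. Both inputs below are assumptions. With T exponential with mean m:
- reported mean = m × (1 − exp(−L/m))
- share still colored at L = exp(−L/m)

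For L = 24 h:
- m = 6: 6 × (1 − e^−4) = 5.9 h, 2% cut
- m = 24: 24 × (1 − e^−1) = 15.2 h, 37% cut
- m = 72: 72 × (1 − e^−0.333) = 20.4 h, 72% cut
- m = 120: 120 × (1 − e^−0.2) = 21.8 h, 82% cut

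Varying L with m = 72 h:

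| L (h) | Reported mean (h) | Still colored at discharge |
|---|---|---|
| 6 | 5.8 | 92% |
| 12 | 11.1 | 85% |
| 24 | 20.4 | 72% |
| 48 | 35.0 | 51% |

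**Step 4: Kaplan-Meier.** The true median is m × ln 2. For m = 72 h it is 49.9 h, beyond all four values of L, so the median is not reached. Censoring avoids treating a cut time as complete but gives no information after discharge.

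**Step 5: follow-up to day 10.** From day 1 to day 10 is (10 − 1) × 24 = 216 h. With L = 216 h:
- m = 24: 24.0 h reported, under 0.1% unresolved
- m = 72: 68.4 h, 5%
- m = 120: 100.2 h, 17%

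**Step 6: masking between doses.** Suppose two dose levels have true means of 24 h and 120 h, a ratio of 120/24 = 5. Cut at 24 h, the reported ratio is 21.8/15.2 = 1.4. Cut at 216 h, it is 100.2/24.0 = 4.2.

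**The case against.** The strongest reply is that the data need not be lost. Coloration is an AE, AEs are collected to the follow-up visit, visit 3 already has an AE assessment and a symptom-directed physical examination, and AE data are listed. On that reading only the dedicated coloration checks end at discharge, and a later stop date can still reach the listing. This stands as far as it goes. A reader might infer that the coloration rule overrides the AE rules, but no passage says so; the defect is a conflict that sites may resolve differently. The reply does not rescue SAP 4.6.1, which ends the duration at discharge whatever the AE record shows.

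A second reply is that color may clear quickly. A reader might infer that injection-site color is likely to outlast the stay, or that duration is understated many-fold. The documents support neither. They give no duration of human skin coloration and no time to discharge. Urine coloration after intravenous dosing was transient (Protocol 2.2.1.2.1.2), and animal skin and urine color disappeared after dosing stopped (2.2.2). Those data do not settle local skin color, but if the true mean is 6 h and discharge comes 24 h after onset, the bias is negligible.

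A third reply concerns the stake. The secondary safety endpoint is the nature, frequency and severity of TEAEs, not their duration. The duration table sits under other endpoints in the SAP. It is not among the named inputs to the optimal dose, although Protocol 4.1 adds safety data in general terms. The protocol names staining as a drawback of existing agents, but the specific benefits in 2.3.2 are shorter operating time and avoided radiation exposure. All of this stands and limits the weight of the point.

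Finally, discharge is not defined, and Protocol 7.3.1 elsewhere speaks of discharge from the study. Read that way, the conflict would disappear. But the coloration rule counts from the end of surgery, so hospital discharge is the natural meaning.

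**Conclusion.** The point holds as an internal conflict with a definite consequence in the SAP. The protocol both ends and continues follow-up of coloration after discharge, and SAP 4.6.1 enters unresolved cases as durations completed at discharge. Followed as written, the descriptive duration is biased downward for every such case and can mask differences in persistence between doses. The conditional Kaplan-Meier analysis only partly corrects this.

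The limit is onset-to-discharge time, which is not the same as length of stay, and it binds only on unresolved cases. It would therefore be too strong to say that the summary simply measures hospital stay. Identical distributions at every dose, or a Kaplan-Meier curve with no events, would require every colored participant to leave hospital still colored.

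The size cannot be determined from the documents. Under the assumed exponential durations and 24 h to discharge it runs from negligible (6 h reported as 5.9 h) to large (120 h reported as 21.8 h). Coloration incidence, the TEAE frequency endpoint and dose selection are not affected. The table should nevertheless be corrected, because as specified it would be misread and the repair is cheap.

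**What to change.** **Protocol.** Reconcile 7.2.6.1, Table 1 footnote 14 and Table 10 footnote 7 with the day 10 rows of Tables 1 and 10 and with 7.3.1 and 7.3.3, so that coloration status and stop date are recorded at the existing visit 3 AE assessment. State that discharge means hospital discharge, if that is intended. For early leavers Table 1 footnote 1 already provides a last assessment: "day 10 outpatient visit procedures will be performed upon study discontinuation". This concerns recording only, not how coloration is managed.

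**SAP 4.6.1.**
- Do not enter a censored time as a completed duration in the descriptive statistics.
- Censor unresolved cases at the last available assessment.
- Report the number unresolved at discharge and at day 10, by dose level and tumor type.

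**Cost.** Wording in three protocol places and one SAP paragraph, plus one status entry at a visit that already takes place. The downside is precision: stop times after discharge will be dates reported by participants, less exact than observed hours. Some cases may also remain unresolved at day 10 (17% in the illustration with a true mean of 120 h), so the censoring rule is still needed.

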7.3 Adverse Events and Other Safety Aspects

The definitions of an AE, SAE or ADE can be found in [Sections [10.3.1](#) Definition of Adverse Events, [10.3.2](#) Definition of Serious Adverse Events and [10.3.3](#) Adverse Device Effect], respectively.

AEs will be reported by the participant (or, when appropriate, by a caregiver, surrogate, or the participant's legally authorized representative), investigator (surgeon) or anesthesiologist.

The investigator and any qualified designees are responsible for detecting, documenting and recording events that meet the definition of an AE, SAE or ADE and remain responsible for following up AEs that are serious, considered related to the study, or that caused the participant to discontinue the IP and/or study [see Section [10.3](#) Appendix 3 Adverse Events/Adverse Device Effects: Definitions and Procedures for Recording, Evaluating, Follow-up and Reporting].

The method of recording, evaluating, and assessing causality of AE, SAE and ADE and the procedures for completing and transmitting SAE/ADE reports are provided in [Section [10.3](#) Appendix 3 Adverse Events/Adverse Device Effects: Definitions and Procedures for Recording, Evaluating, Follow-up and Reporting].

7.3.1 Time Period and Frequency for Collecting Adverse Event and Serious Adverse Event Information

All SAEs will be collected from the signing of the ICF until the follow-up visit at the time points specified in the Schedule of Assessments [[Table 1](#)] and reported on the eCRF.

All AEs will be collected from the signing of the ICF until the follow-up visit at the time points specified in the Schedule of Assessments [[Table 1](#)] and reported on the eCRF.

If the NCI CTCAE grade of an SAE/AE changes, the event should be relisted on the eCRF with the new NCI CTCAE grade and new onset date.

If the NCI CTCAE grade decreases, the SAE/AE should be relisted on the eCRF with the new NCI CTCAE grade and new onset date. The exception is ongoing pre-dose events that continue post-dose and improve post-dose. Such events should not be re-listed.

If the NCI CTCAE grade of an SAE reduces, the details of the AE should be provided on the SAE worksheet for the medical assessor to be able to assess the course of the event.

All SAEs will be recorded and reported to the sponsor or designee immediately and under no circumstance should this exceed 24 hours, as indicated in [Section 10.3 Appendix 3 Adverse Events/Adverse Device Effects: Definitions and Procedures for Recording, Evaluating, Follow-up and Reporting]. The investigator will submit any updated SAE data to the sponsor within 24 hours of it being available.

Investigators are not obligated to actively seek AE or SAE after conclusion of the study participation. However, if the investigator learns of any SAE, including a death, at any time after a participant has been discharged from the study, and he/she considers the event to be reasonably related to the study IP or study participation, the investigator must promptly notify the sponsor.

The Reference Safety Information that will be used to determine expectedness of an SAE for this study is in the IB.

7.3.1.1 Adverse Device Effects

- ADEs are to be collected via the ADE worksheet and reported to the sponsor within 24 hours of awareness (see [Section 10.3.3.1]).
- Any complaint about a device must be reported regardless of whether the defect or deficiency had any effect on a participant or on study personnel (see [Section 10.3.3.3]).

7.3.2 Method of Detecting Adverse Events and Serious Adverse Events

Care will be taken not to introduce bias when detecting AEs and/or SAEs. Open-ended and non-leading verbal questioning of the participant is the preferred method to inquire about AE occurrences.

7.3.3 Follow-up of Adverse Events and Serious Adverse Events

After the initial AE/SAE report, the investigator is required to proactively follow each participant at subsequent visits/contacts. All SAEs will be followed until resolution, stabilization, the event is otherwise explained, or the participant is lost to follow-up (as defined in [Section 8.3 Lost to Follow-up]). Further information on follow-up procedures is provided in [Section 10.3 Appendix 3 Adverse Events/Adverse Device Effects: Definitions and Procedures for Recording, Evaluating, Follow-up and Reporting].

If after the protocol-defined AE collection period (see [Section 7.3.1 Time Period and Frequency for Collecting Adverse Event and Serious Adverse Event Information]), an AE progresses to an SAE, or the investigator learns of any (S)AE (serious adverse event or adverse event) including death, where he/she considers there is reasonable possibility it is related to the IP or study participation, the investigator must promptly notify the sponsor.

7.3.4 Regulatory Reporting Requirements for Serious Adverse Events/Adverse Device Effects

- Prompt notification by the investigator to the sponsor of a SAE/ADE is essential so that legal obligations and ethical responsibilities towards the safety of participants and the safety of a study IP under clinical investigation are met.
- The sponsor has a legal responsibility to notify both the local regulatory authority and other regulatory agencies and/or device manufacturer about the safety of a study IP under clinical investigation. The sponsor will comply with country-specific regulatory requirements relating to safety reporting to the regulatory authority, IRB/IEC and investigators.
- Investigator safety reports must be prepared for suspected unexpected serious adverse reactions (SUSAR) according to local regulatory requirements and sponsor policy and forwarded to investigators as necessary.
- An investigator who receives an investigator safety report describing a SAE or other specific safety information (e.g., summary or listing of SAEs) from the sponsor will review and then file it along with the IB and will notify the IRB/IEC, if appropriate according to local requirements.

7.3.5 Disease-related Events and/or Disease-related Outcomes Not Qualifying as Adverse Events or Serious Adverse Events

Under this protocol, the following event will not be considered as an (S)AE:

- Preplanned and elective hospital/clinical procedures/interventions or procedures for diagnostic, therapeutic or surgical procedures for a preexisting condition that did not worsen during the course of the study. These procedures are collected in the eCRF.

7.3.6 Special Situations

Certain special situations observed in association with the IP, such as incorrect administration (e.g., wrong dose of IP or background therapy) are reported as protocol deviations and/or may require special reporting, as described below. These special situations are not considered AEs but do require to be communicated to Astellas as per the timelines defined below.

If a special situation is associated with, or results in, an AE, the AE is to be assessed separately from the special situation and captured as an AE in the eCRF. If the AE meets the definition of an SAE, the SAE is to be reported as described in [Section 10.3.7 Reporting Procedures for Serious Adverse Events/Adverse Device Effects] and the details of the associated special situation are to be included in the clinical description on the special situation worksheet or pregnancy reporting form.

The special situations are:

- Pregnancy
- Medication error, overdose and use outside protocol
- Misuse/abuse
- Occupational exposure

- (Suspicion of) Transmission of infectious agent
- Suspected drug-drug interaction

Instructions and procedures for reporting special situations are provided in [Section 10.3.8 Reporting Procedures for Pregnancy and Special Situations].

